7. ASSESSMENTS

Every effort should be made to ensure that the protocol-required tests and procedures are completed as described. However, it is anticipated that from time to time there may be circumstances outside of the control of the investigator that may make it unfeasible to perform the test. In these cases the investigator will take all steps necessary to ensure the safety and well-being of the subject. When a protocol-required test cannot be performed, the investigator will document the reason for this and any corrective and preventive actions that he or she has taken to ensure that normal processes are adhered to as soon as possible. The study team will be informed of these incidents in a timely manner.

7.1. Safety Parameters

Safety parameters will be assessed as described in the Schedule of Activities, Section 8, and below.

A medical history, physical examination, and measurement of rectal temperature will be performed on all subjects prior to Dose 1 of c7vPnC in Groups 1 and 2 and the first dose of Prevnar 13 in Group 3 to determine subject eligibility and to establish a clinical baseline. Significant medical history and clinically significant observations from the physical examination and temperature measurement will be documented and recorded in the CRF.

Acute reactions within the first 30 minutes after Doses 1 to 4, the c7vPnC Supplemental Dose (Group 3), and concomitant vaccine administration (Groups 1 and 3) will be assessed and documented as an AE or SAE in the CRF, as appropriate. Prompted e-diary events, including local reactions (pain, redness, and swelling) and systemic events (fever, decreased appetite, drowsiness/increased sleep, and irritability) that occur in the 7 days after Doses 1 to 4 and the Supplemental Dose, are graded as described in Section 7.1.2.

7.1.1. Subject Electronic Diary

The subject's legally acceptable representative will be asked to monitor and record local reactions, specific systemic events, and antipyretic/pain medication taken for 7 days, each evening following Doses 1 to 4 and the Supplemental Dose using an e-diary (in a provisioned device or an application on a personal device), which allows recording of these assessments only within a fixed time window, thus providing the accurate representation of the subject's experience at that time. Data on local reactions, specific systemic events, and antipyretic/pain medication reported in the e-diary will be transferred electronically to the e-diary vendor, where they will be available for review by investigators, their qualified designees, and sponsor staff at all times via an internet-based portal. At intervals agreed to

by the vendor and Pfizer, these data will be transferred electronically to Pfizer for analysis and reporting.

The daily e-diary data will not be captured in the CRF. However, if a subject withdraws because of prompted events reported in the e-diary, the event(s) should be recorded on the AE page of the CRF, regardless of whether the investigator considers the event(s) to be clinically significant.

The investigator or designee must obtain stop dates for any reactions ongoing on the last day that the e-diary was completed. The stop dates should be entered in the CRF.

Investigators (or an appropriately qualified designee) are required to review the e-diary data online at frequent intervals (daily is optimal) to evaluate subject compliance and reported events as part of the ongoing safety review.

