	Visit	Visit	Visit	Visit	Visit	Visit		Month	Visit		19-Month
								Visit			Phone
											Contact
Visit Window (Days)	Day 1	21 to 35	42 to 63	21 to 35	42 to 63	21 to 35	28 to 42	365 to	21 to 35	28 to 42	168 to
		Days	Days	Days	Days	Days	Days	386 Days	Days	Days	196 Days
		After	After	After	After	After	After	of Age	After	After	After
		Prevnar	Prevnar	Prevnar	Prevnar	Prevnar	Dose 3		Prevnar	Dose 4	Dose 4
		13 at			13 at						
		Visit 1	Visit 1	Visit 3	Visit 3	Visit 5			Visit 8		
Review e-diary events ^{d,e}			X		X		X			X	
Collect e-diary (if device provided)							X			X	
Record and report adverse events	XX XX										
Record and report serious adverse events and newly diagnosed chronic medical conditions ^{f,g}	X-										·-X

Abbreviations: DTaP = diphtheria, tetanus, and acellular pertussis; e-diary = electronic diary; NDCMC = newly diagnosed chronic medical condition.

- a. Blood sample will be collected prior to vaccination.
- b. The subject may receive vaccines with inactivated poliovirus, hepatitis B, or *Haemophilus influenzae* type b (either separately or in the diphtheria, tetanus, and pertussis combination vaccine) at 2, 4, and 6 months of age. Measles, mumps, and rubella (MMR) vaccination may be administered concomitantly at 12 months of age or according to the permitted treatment windows in Section 5.7.3. Rotavirus vaccine may be administered orally at any time.
- c. The subject's legally acceptable representative will record prompted local reactions and systemic events in an e-diary for the 7 days following each dose of c7vPnC. The subject's legally acceptable representative will be instructed to contact the study staff if the subject experiences redness or swelling >14 caliper units, severe pain at the injection site, or a fever >104.0°F (>40.0°C), or has an emergency room visit or hospitalization.
- d. Designated site staff will review e-diary data online at frequent intervals (daily is optimal) for the 7 days following each dose of c7vPnC to evaluate subject compliance and reported events as part of the ongoing safety review.
- f. Record concomitant medications used to treat SAEs and NDCMCs as described in Section 5.7.4.
- g. A newly diagnosed chronic medical condition is defined as a disease or medical condition, not previously identified, that is expected to be persistent or otherwise long-lasting in its effects.

$Group\ 3-Control\ Group\ With\ Supplemental\ Dose$

Visit Number	1	2	3	4	5	6	7	8

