3. STUDY DESIGN

This will be a Phase 2, multicenter, randomized, active-controlled, open-label study with a 3-arm parallel design, conducted at investigator sites in the United States. A total of 565 infants \ge 42 to \le 98 days of age at the time of consent will be enrolled and randomized in a 1:1:1 ratio to receive a vaccine series with:

- c7vPnC coadministered with Prevnar 13 (Group 1 coadministration);
- c7vPnC given 1 month after Prevnar 13 (Group 2 staggered administration); or
- Prevnar 13 alone as the active control group (Group 3 control with Supplemental Dose).
 A single dose of c7vPnC will be administered after the Prevnar 13 series is completed in this group.

In all groups, Prevnar 13 will be administered at 2, 4, 6, and 12 months of age. c7vPnC will be administered at 2, 4, 6, and 12 months of age in Group 1; at 3, 5, 7, and 13 months of age in Group 2; and at 13 months of age in Group 3. **Note:** In this document, and related study documents, vaccine (investigational product) Doses 1, 2, 3, and 4 specifically refer to the doses of c7vPnC administered in Groups 1 and 2, or the doses of Prevnar 13 administered in the control group (Group 3). The dose of c7vPnC administered in Group 3 will be referred to as the Supplemental Dose. See Table 1 for a summary of study groups and key procedures.

Table 1. Summary of Study Groups and Key Procedures

·	2 mo/o	3 mo/o	4 mo/o	5 mo/o	6 mo/o	7 mo/o	8 mo/o	12 mo/o	13 mo/o	14 mo/o	18 mo/o	19 mo/o
Group 1 Coadmin. c7vPnC (n= ~188)	c7vPnC Dose 1 Prev13		c7vPnC Dose 2 Prev13		c7vPnC Dose 3 Prev13	Blood draw		Blood draw c7vPnC Dose 4 Prev13	Blood draw		Phone contact	
Group 2 Staggered c7vPnC (n= ~188)	Prev13	c7vPnC Dose 1	Prev13	c7vPnC Dose 2	Prev13	Blood draw c7vPnC Dose 3	Blood draw	Prev13	Blood draw c7vPnC Dose 4	Blood draw		Phone contact
Group 3 Control (n= ~188)	Prev13 Dose 1		Prev13 Dose 2		Prev13 Dose 3	Blood draw		Blood draw Prev13 Dose 4	Blood draw c7vPnC Suppl. Dose	CCI		Phone contact

Abbreviations: Coadmin. = coadministered; mo/o = months old; Prev13 = Prevnar 13; Suppl. = supplemental.

Vaccine containing diphtheria, tetanus, and acellular pertussis antigens will be administered at 2, 4, and 6 months of age. This is as part of routine standard of care in the United States,

Other routine pediatric vaccines may be administered in this study, with or without certain restrictions.

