- Ensure and document that the subject continues to be eligible for the study (see Section 6.5 for withdrawal information).
- Record vaccines administered since Visit 2 as described in Section 5.7.4.
- Review the subject's e-diary data with the subject's legally acceptable representative; collect stop dates of any e-diary events ongoing on the last day that the e-diary was completed and record stop dates in the CRF.
- Determine whether any AEs (includes nonserious AEs, SAEs, and NDCMCs) have occurred since the previous visit and follow up on any previously reported events to determine the outcome (ie, record stop dates or confirm if they are still continuing) and record as described in Section 8, and record concomitant medications used to treat SAEs and NDCMCs.
- Administer a single 0.5-mL injection of Prevnar 13 into the right anterolateral thigh.
- Administer DTaP-containing vaccine and other permitted vaccines (to be administered into a limb other than the left leg).

After vaccination:

- Remind the subject's legally acceptable representative to contact the investigator or investigator site staff as soon as possible if any significant illness or medical event (eg, emergency room visit or hospitalization) occurs during the study period.
- Remind the subject's legally acceptable representative that use of prophylactic antipyretic/pain medication, while permitted, is not recommended on the day of investigational product administration (before or after vaccination).
- The investigator or an authorized designee completes the CRF and updates the investigational product accountability records.

6.2.4. Group 2 Visit 4 (c7vPnC Dose 2: 5-Month Visit, 21 to 35 Days After Prevnar 13 at Visit 3)

- Ensure and document that the subject continues to be eligible for the study (see Section 6.5 for withdrawal information), and none of the temporary delay criteria are met.
- Record vaccines administered since Visit 3 as described in Section 5.7.4.
- Determine whether any AEs (includes nonserious AEs, SAEs, and NDCMCs) have occurred since the previous visit and follow up on any previously reported events to determine the outcome (ie, record stop dates or confirm if they are still continuing) and record as described in Section 8, and record concomitant medications used to treat SAEs and NDCMCs.
- Measure and record the subject's rectal temperature ($^{\circ}F/^{\circ}C$).
- Administer a single 0.5-mL injection of c7vPnC into the left anterolateral thigh.

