9.4. Safety Analysis

All safety analyses will be performed using the safety population.

Descriptive statistics for local reactions for the c7vPnC injection site in Groups 1 and 2 and the Supplemental Dose in Group 3, as well as the Prevnar 13 site in Group 3, and systemic events from Day 1 to Day 7 will be presented by severity and cumulatively across severity levels. Descriptive statistics will include proportions of subjects with the indicated endpoint and the associated Clopper-Pearson 95% CIs. Local reactions will be compiled for each dose for each group (Doses 1, 2, 3, and 4 and the Supplemental Dose) separately and compiled across all 4 doses of the same group.

AEs (including nonserious AEs, SAEs, and NDCMCs) will be compiled over 2 intervals: from Dose 1 to 1 month following Dose 3 and from Dose 4 to 1 month following Dose 4/Supplemental Dose. SAEs and NDCMCs will be summarized from Dose 1 until 6 months after Dose 4/Supplemental Dose. The descriptive statistics for AEs will be summarized as the number and percentage of subjects reporting at least 1 event of each preferred term with the associated Clopper-Pearson 95% CIs, arranged by system organ class.

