6.1.3. Adverse Events

6.1.3.1. Primary Analysis

Endpoint: Proportions of subjects reporting AEs from Dose 1 to 1 month following Dose 3, from Dose 4 to 1 month following Dose 4, and from Supplemental Dose to 1 month following Supplemental Dose

- Analysis time points: Dose 1 to 1 month after Dose 3, and from Dose 4 to 1 month after Dose 4/Supplemental Dose
- Analysis population: Dose 1 to Dose 3 safety population, Dose 4 safety population, Supplemental dose safety population for supplemental Dose
- Analysis methodology: Descriptive statistics
- Supporting objective: Primary Objective

Reporting results:

The percentage (%), number of subjects and the denominator (N) used in the percentage calculation, and corresponding 95% Clopper-Pearson CI will be presented for each vaccine group.

Figures: None

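### Systemic reactions after the 4- and 6-month Prevnar 13/DTaP visits are diary events in Groups 1 and 3 but can only be AEs in Group 2, so the first-interval AE proportion is not like for like

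*Protocol*

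**What the plan says.** Protocol Section 3 fixes the dose numbering: "Doses 1, 2, 3, and 4 specifically refer to the doses of c7vPnC administered in Groups 1 and 2". In Group 3 the numbered doses are Prevnar 13. Section 7.1.1 has the diary completed "each evening following Doses 1 to 4 and the Supplemental Dose using an e-diary". For Group 2, footnote c of the Schedule of Activities has the parent or guardian "record prompted local reactions and systemic events in an e-diary for the 7 days following each dose of c7vPnC". Section 5.4 places Group 2's concomitant injectables, DTaP included, at the Prevnar 13 visits and not at the c7vPnC visits.

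On the route from diary to AE page, Section 7.1.1 says "The daily e-diary data will not be captured in the CRF". The exceptions given are withdrawal because of a prompted event (7.1.1) and Grade 4 events (7.1.2).

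At Group 2 Visits 4 and 6, each the next visit after a Prevnar 13/DTaP visit, the site must "Determine whether any AEs (includes nonserious AEs, SAEs, and NDCMCs) have occurred since the previous visit" (Sections 6.2.4 and 6.2.6).

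SAP 6.1.3.1 defines the primary AE endpoint for the first interval as "Proportions of subjects reporting AEs from Dose 1 to 1 month following Dose 3", reported once per vaccine group. Protocol 9.4 plans "Descriptive statistics for local reactions for the c7vPnC injection site in Groups 1 and 2"; for Group 3 it takes the Prevnar 13 site and the Supplemental Dose site.

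**The concern.** The trial's title question is c7vPnC given with, or separately from, Prevnar 13. The AE proportion is a primary endpoint shown for each group, and the data are meant to inform the Phase 3 design. Readers will compare coadministration with staggering on these tables.

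In Groups 1 and 3, Prevnar 13 and DTaP are given on the day of a numbered dose, so a fever in the following week goes to the diary. In Group 2 the same vaccines are given about a month before c7vPnC, with no diary. A fever in that week is either reported at the next visit and counted as an AE, or it appears in no table. In the first case Group 2's AE proportion contains events of a kind largely kept out of the other two arms. In both cases Group 2's prompted systemic rates omit reactions that Groups 1 and 3 include. A difference between arms could then reflect how events were captured and not how the infants fared.

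**Working it through.** **Which visits are affected.** Setting the Schedule of Activities beside Sections 6.2.1 to 6.2.9:

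| Prevnar 13 visit | DTaP given | Diary after it, Groups 1 and 3 | Diary after it, Group 2 | Group 2: nonserious AEs asked for at next visit | Inside Group 2's AE endpoint |
|---|---|---|---|---|---|
| 2 months | yes | yes | no | yes (Visit 2) | no, before Dose 1 |
| 4 months | yes | yes | no | yes (Visit 4) | yes |
| 6 months | yes | yes | no | yes (Visit 6) | yes |
| 12 months | no | yes | no | no, SAEs and NDCMCs only (Visit 9) | no, before Dose 4 |

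Two visits therefore count, both in the first AE interval.

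**Could a c7vPnC diary spill over onto a Prevnar 13 visit?** Not within the visit windows. c7vPnC is given at most 35 days after one Prevnar 13 dose, and the next Prevnar 13 dose comes at least 42 days after it. A diary that starts on day 35 covers days 35 to 41 and closes before day 42.

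**Local reactions.** Only the left-thigh product is analysed. The Prevnar 13 site (right thigh) is outside the analysis in both Group 1 and Group 2, and DTaP is never given in the left leg. The only contrast is Group 3, whose Prevnar 13 site is analysed.

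**Size.** The documents give no figure for this shift. Their one related figure, Protocol Table 5, reproduces: 1 − (1 − p)^188 gives 0.610, 0.849 and above 0.999 at p = 0.5%, 1% and 5%. It does not address how events are classified.

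Inputs:
- k = 2 visits, from the table above.
- n = 188 planned per arm (Protocol 9.1).
- q = chance that an infant has such a reaction recorded as an AE after one visit. Assumed 2%, 5% or 10%.
- b = proportion with some other AE in the interval. Assumed 40% to 70%.
- Visits independent of each other and of the other AEs (assumed).

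Proportion with at least one such AE: 1 − (1 − q)^2. Rise in the any-AE proportion: (1 − b) × [1 − (1 − q)^2].

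| q | 1 − (1 − q)^2 | Rise at b = 40% | Rise at b = 70% |
|---|---|---|---|
| 2% | 0.0396 | 0.60 × 0.0396 = 2.4 points | 0.30 × 0.0396 = 1.2 points |
| 5% | 0.0975 | 5.9 points | 2.9 points |
| 10% | 0.1900 | 11.4 points | 5.7 points |

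If the same infants reacted at both visits, the rise would fall towards (1 − b) × q: at q = 10% and b = 40% it would be 6.0 points, not 11.4.

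**Against sampling error.** The 95% half-width for a two-arm difference is 1.96 × √(2b(1 − b)/188): 9.9 points at b = 40%, 10.1 at 50% and 9.3 at 70%. The low scenarios sit well inside this width. Only the top one exceeds it.

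**The case against.** Several objections have force.

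- **AE entry in Group 2 is inferred.** No sentence directs sites to enter post-Prevnar 13 reactions as AEs. Section 8.2.1 says typical fussiness or crying is generally not an AE, so a reader who takes all irritability after these visits to become an AE goes too far. Fever and refusal to feed are harder to set aside on that ground. If sites enter nothing, the AE inflation disappears, but the gap in Group 2's prompted rates remains.
- **The exclusion in Groups 1 and 3 is also partly inferred.** The sentence in 7.1.1 concerns diary data. It does not state that a prompted event may never also be recorded as an AE. The two named exceptions imply that this is the general rule.
- **The direction is not purely one-way.** A reader might infer that staggering must look worse on AEs. Under Section 7.1, acute reactions within 30 minutes of concomitant vaccines are documented as AEs in Groups 1 and 3 only, and the Schedule of Activities has no such observation at Group 2's Prevnar 13 visits. That pulls the other way.
- **A broader reading fails.** A reader might infer that all Prevnar 13 and DTaP reactions, local ones included, are split this way between Group 2 and the other two arms, or that both AE intervals are affected. The site rules in 5.4 and 9.4 rule out the first, and the timing of the 2- and 12-month visits rules out the second.
- **Preferred-term tables are already planned** (Protocol 9.4), and an excess of fever in Group 2 would show there. But they do not tie onset to a Prevnar 13 visit, and they give no any-AE proportion without these events.
- **Some SAP text around the AE analysis is redacted** and may deal with this.
- **The study is descriptive,** with no tests or decision rules. No error rate is at stake, only the reading across arms.

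**Conclusion.** The point holds for systemic reactions after two visits and for one AE interval. Group 2's AE proportion from Dose 1 to 1 month after Dose 3 is not comparable with that of Groups 1 and 3. Its prompted systemic rates describe c7vPnC visits and not the whole staggered regimen. For local reactions the contrast is with Group 3 alone.

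The size is uncertain: about 1 to 11 percentage points under the assumed reporting rates and background, with the visits treated as independent. That ranges from negligible to about the precision of a two-arm comparison. It deserves correction because the comparison affected is the one the trial was set up to describe, and because the visible text makes no allowance for it.

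**What to change.** In SAP 6.1.3.1, for the interval from Dose 1 to 1 month after Dose 3:

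1. Keep the all-AE proportion as planned.
2. Add a supplementary proportion, defined identically in every group, that excludes AEs whose preferred term matches a prompted event (fever, decreased appetite, drowsiness, irritability, injection-site redness, swelling or pain) with onset on Days 1 to 7 after any study-visit vaccination, Group 2's Prevnar 13 visits included.
3. State that the supplementary proportion is the one to use when AE rates are read across groups.
4. Footnote the prompted-event tables: Group 2's rates cover c7vPnC visits only.

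The cost is one extra table and a footnote. The table uses AE onset dates, coded terms and vaccination dates that the trial already collects, so no new data and no change to visits are needed. The supplementary proportion cannot recover the Group 2 reactions that no diary captured, which is why the footnote is needed as well. Nothing is hidden, because the all-AE proportion stays and SAEs keep their own analysis in SAP 6.1.4.

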7.1.2. Grading Scale for Prompted Events

The grading scales used in this study to assess prompted events as described below are based on concepts outlined in the Food and Drug Administration (FDA) Center for Biologics Evaluation and Research (CBER) guidelines on toxicity grading scales for adults and adolescent volunteers enrolled in preventive vaccine clinical trials, but have been adapted for applicability to healthy infants.⁶⁹

7.1.2.1. Local Reactions

For the first 7 days following Doses 1 to 4 and the Supplemental Dose, the subject's legally acceptable representative will be asked to assess redness, swelling, and pain at the injection site and to record the symptoms in the e-diary in the evening. Redness and swelling will be measured and recorded in measuring device units (range: 1 to >14; an entry in the e-diary of 15 will denote >14), and then categorized during analysis as mild, moderate, or severe based on the grading scale in Table 2 below. Measuring device units can be converted to centimeters according to the following scale: 1 measuring device unit = 0.5 cm. Pain at the vaccine injection site will be assessed by the subject's legally acceptable representative as mild, moderate, or severe according to the grading scale in Table 2 below. The subject's legally acceptable representative will be prompted to contact the investigator if the subject experiences a severe (Grade 3 or above) local reaction to assess the reaction and perform an unscheduled assessment or visit as appropriate.

Only an investigator is able to classify a subject's local reaction as Grade 4, after physical examination of the subject or documentation from another medically qualified source (eg, emergency room or hospital record). If a subject experiences a Grade 4 local reaction, the investigator must immediately notify the sponsor. Site staff will educate the subject's legally acceptable representative regarding signs and symptoms that would prompt site contact.

The procedure for notification of the sponsor is provided in the study reference manual (SRM) or equivalent.

Table 2. Grading Scales for Local Reactions

	Mild Grade 1	Moderate Grade 2	Severe Grade 3 ^a	Grade 4 ^b
Redness (synonymous with erythema)	1 to 4 caliper units (or measuring device units)	5 to 14 caliper units (or measuring device units) =	>14 caliper units (or measuring device units) =	Necrosis or exfoliative dermatitis
Swelling (synonymous with edema)	0.5 to 2.0 cm 1 to 4 caliper units (or measuring device units) = 0.5 to 2.0 cm	>2.0 to 7.0 cm 5 to 14 caliper units (or measuring device units) = >2.0 to 7.0 cm	>7 cm >14 caliper units (or measuring device units) = >7 cm	Necrosis
Pain at injection site (tenderness)	Hurts if gently touched (eg, whimpers, winces, protests, or withdraws)	Hurts if gently touched, with crying	Causes limitation of limb movement	Emergency room visit or hospitalization for severe pain (tenderness) at injection site

Abbreviations: CRF = case report form; e-diary = electronic diary.

Note: If the size of the redness and/or swelling falls between 2 measuring device units, the higher measuring device unit number will be recorded in the e-diary.

- a. Legally acceptable representatives of the subjects experiencing local reactions >14 caliper units (>7.0 cm) are to be contacted by the study site. An unscheduled visit may be required.
- b. Grade 4 assessment should be made by the investigator. Grade 4 will not be collected in the e-diary but as an AE on the CRF. The severity of the local reaction should be graded using the AE severity grading scale in Section 8.3.

